7.0 FEASIBILITY OUTCOME MEASURES

Feasibility outcomes will be analyzed using descriptive statistics, reported as count and percentage or mean and standard deviation depending on the type of variable to summarize the FAITH-2 feasibility outcomes of 1) initiation of clinical sites (locations and timelines), 2) rate of participant enrolment, 3) rate of protocol adherence (the number of errors in randomization, 4) the number of crossovers between SHS and cancellous screw treatment groups, 5) adherence to the daily vitamin D supplementation), 6) proportion of participants with complete follow-up at 12 months post-fracture, 7) and level of data quality (**Table 8**).

Table 8: Feasibility Outcomes

Feasibility Outcomes	Variable	N=
Time to Initiation of Clinical Sites, median (IQR) (months)	Clinical site initiation tracker	
Time to Enroll 60 Participants, n (months)	2.1 Q5 of first and last enrolled participant	
Rate of Protocol Adherence: Number of Errors in Randomization, n (%)	14.1 Q2	
Rate of Protocol Adherence: Number of Crossovers between SHS and CS treatment groups, n (%)	5.1 Q1, 6.1 Q1	
Rate of Protocol Adherence: Adherence to the daily vitamin D supplementation, n (%)	8.2 Q10/Q11 (6 weeks, 3 months, 6 months)	
Proportion of Participants with Complete Follow-up at 12 Months Post-Fracture, n (%)	8.1 (12 months)	
Level of Data Quality, n (%)	Completeness of CRFs	

8.0 PRIMARY CLINICAL ENDPOINT

The primary analyses will first be completed using only blinded treatment groups. All outcome analyses will be performed using the intention to treat approach. The FAITH-2 study primary clinical endpoint is a composite of patient important outcomes that occur within the 12 months post-surgery follow-up period (**Table 9**). Specifically, these are limited to 1) re-operation, 2) femoral head osteonecrosis, 3) severe femoral neck malunion, and 4) nonunion.

The first analysis of clinical outcomes will be a Cox regression with main effects for implant type and supplementation, and the interaction between the two. If the interaction is not significant at $\alpha=0.05$ we will perform two independent comparisons between the treatment groups (SHS versus cancellous screws AND separately vitamin D₃ supplementation versus placebo) using the chi-square statistic and an alpha level of 0.05 for the composite of patient important outcomes (**Tables 10 and 11**).

If the interaction is significant we will keep this interaction term in all subsequent analyses, and present two hazard ratios (HRs) with 95% confidence intervals (CIs) for the surgical intervention and two HRs for the nutritional supplementation (i.e. We will report an HR for SHS versus cancellous screws in those who receive vitamin D, and a separate HR for SHS versus cancellous screws in those who receive placebo. We will also report an HR for vitamin D versus placebo in those who receive SHS, and a separate HR for vitamin D versus placebo in those who receive cancellous screws) The results will be summarized in **Table 12**. Kaplan-Meier curves will also be constructed.

Table 9: Primary Clinical Endpoint Components and Reasons for Secondary Procedures

Outcome	Definition
Unplanned Secondary Procedures (study event)	
Any unplanned surgery related to the treatment of the femoral neck fracture. Specific unplanned secondary procedures include:
 
 • Implant removal • Bone graft • Wound closure • Proximal femur osteotomy • Implant exchange – THA • Implant exchange – HA • Implant exchange – CS • Implant exchange – SHS • Implant exchange – Other IF • Soft tissue procedure • Dynamization • Osteochondroplasty
Reasons for Secondary Procedures	
 • Shortening • Nonunion • Femoral head osteonecrosis • Deep infection • Superficial infection • Painful implant • Implant failure/breakage • Hip dislocation • Peri-prosthetic femur fracture • Hip instability • Wound healing problem • Screw penetration • Screw cut-out • Post traumatic arthritis • IT Fracture • Relieve pain
Femoral Head Necrosis	Any evidence of osteonecrosis on any follow-up medical imaging study (i.e., radiographs, magnetic resonance imaging (MRI), or other advanced imaging study)
Severe Femoral Neck Malunion	Fracture healing with femoral neck shortening of >10 mm in any plane on follow-up x-rays ¹
Nonunion	Failure of the fracture to progress towards healing defined as a Radiographic Union Score for Hip (RUSH) ^{2,3} score below a pre-determined threshold specific for nonunion at 6 months or greater post-injury.

Table 10: Primary Clinical Endpoint, According to Surgical Treatment (No Significant Interaction Between Implant Type and Supplementation Present)

End Point	Variable	Overall N=	Surgical Treatment X N=	Surgical Treatment Y N=	P-Value
Primary Clinical Endpoint of Re-operation					
Re-operation	Adjudicated Data				
Procedure for Nonunion Implant removal Bone graft Proximal femur osteotomy Implant exchange – THA Implant exchange – IF	Adjudicated Data				
Procedure for Femoral Head Osteonecrosis Implant removal Implant exchange – THA	Adjudicated Data				
Procedure for Deep Infection Wound closure Implant exchange – SHS Soft tissue procedure	Adjudicated Data				
Procedure for Painful Hardware Implant removal Bone graft Implant exchange – THA	Adjudicated Data				
Procedure for Screw Penetration Implant removal	Adjudicated Data				
Procedure for Post-Traumatic Arthritis Osteochondroplasty	Adjudicated Data				
Procedure for IT Fracture Implant exchange – IF	Adjudicated Data				
Procedure for Relieving Pain Implant exchange – THA	Adjudicated Data				
Femoral head osteonecrosis					
Femoral head osteonecrosis	Adjudicated Data				
Severe femoral neck malunion					
Severe femoral neck malunion	Adjudicated Data				
Nonunion					
Nonunion	Adjudicated Data				

Table 11: Primary Clinical Endpoint, According to Nutritional Supplementation (No Significant Interaction Between Implant Type and Supplementation Present)

End Point	Variable	Overall N=	Nutritional Supplementation X N=	Nutritional Supplementation Y N=	P-Value
Primary Clinical Endpoint of Re-operation					
Re-operation	Adjudicated Data				
Procedure for Nonunion Implant removal Bone graft Proximal femur osteotomy Implant exchange – THA Implant exchange – IF	Adjudicated Data				
Procedure for Femoral Head Osteonecrosis Implant removal Implant exchange – THA	Adjudicated Data				
Procedure for Deep Infection Wound closure Implant exchange – SHS Soft tissue procedure	Adjudicated Data				
Procedure for Painful Hardware Implant removal Bone graft Implant exchange – THA	Adjudicated Data				
Procedure for Screw Penetration Implant removal	Adjudicated Data				
Procedure for Post-Traumatic Arthritis Osteochondroplasty	Adjudicated Data				
Procedure for IT Fracture Implant exchange – IF	Adjudicated Data				
Procedure for Relieving Pain Implant exchange – THA	Adjudicated Data				
Femoral head osteonecrosis					
Femoral head osteonecrosis	Adjudicated Data				
Severe femoral neck malunion					
Severe femoral neck malunion	Adjudicated Data				
Nonunion					
Nonunion	Adjudicated Data				

Table 12: Primary Clinical Endpoint (Significant Interaction Between Implant Type and Supplementation Present)

End Point	Variable	Overall N=	Surgical Treatment X N=	Surgical Treatment Y N=	Nutritional Supplementation X N=	Nutritional Supplementation Y N=	Hazard Ratio (95% CI)				P- Value
							Surgery X + Supplement X vs. Surgery Y + Supplement X	Surgery X + Supplement Y vs. Surgery Y + Supplement Y	Surgery X + Supplement X vs. Surgery X + Supplement Y	Surgery Y + Supplement X vs. Surgery Y + Supplement Y	
Primary Clinical Endpoint: re-operation, femoral head osteonecrosis, severe femoral neck malunion, nonunion	Adjudicated Data										
Primary Clinical Endpoint Components											
Malunion Implant removal Bone graft Wound closure Proximal femur osteotomy Implant exchange – THA Implant exchange – HA Implant exchange – IF (crossover) Implant exchange – IF (original) Implant exchange – Intramedullary nailing Implant exchange – curved plate and IF Implant exchange – 110 degree blade plate Soft tissue procedure Dynamization Osteochondroplasty	Adjudicated Data										
Nonunion Implant removal	Adjudicated Data										

Bone graft Wound closure Proximal femur osteotomy Implant exchange – THA Implant exchange – HA Implant exchange – IF (crossover) Implant exchange – IF (original) Implant exchange – Intramedullary nailing Implant exchange – curved plate and IF Implant exchange – 110 degree blade plate Soft tissue procedure Dynamization Osteochondroplasty											
Femoral Head Osteonecrosis Implant removal Bone graft Wound closure Proximal femur osteotomy Implant exchange – THA Implant exchange – HA Implant exchange – IF (crossover) Implant exchange – IF (original) Implant exchange – Intramedullary nailing Implant exchange – curved plate and IF Implant exchange –	Adjudicated Data										

110 degree blade plate Soft tissue procedure Dynamization Osteochondroplasty											
Deep Infection Implant removal Bone graft Wound closure Proximal femur osteotomy Implant exchange – THA Implant exchange – HA Implant exchange – IF (crossover) Implant exchange – IF (original) Implant exchange – Intramedullary nailing Implant exchange – curved plate and IF Implant exchange – 110 degree blade plate Soft tissue procedure Dynamization Osteochondroplasty	Adjudicated Data										
Superficial Infection Implant removal Bone graft Wound closure Proximal femur osteotomy Implant exchange – THA Implant exchange – HA Implant exchange – IF (crossover) Implant exchange – IF (original)	Adjudicated Data										

Implant exchange – Intramedullary nailing Implant exchange – curved plate and IF Implant exchange – 110 degree blade plate Soft tissue procedure Dynamization Osteochondroplasty											
Painful Hardware Implant removal Bone graft Wound closure Proximal femur osteotomy Implant exchange – THA Implant exchange – HA Implant exchange – IF (crossover) Implant exchange – IF (original) Implant exchange – Intramedullary nailing Implant exchange – curved plate and IF Implant exchange – 110 degree blade plate Soft tissue procedure Dynamization Osteochondroplasty	Adjudicated Data										
Hardware Failure/Breakage Implant removal Bone graft Wound closure Proximal femur osteotomy Implant exchange – THA	Adjudicated Data										

Implant exchange – HA Implant exchange – IF (crossover) Implant exchange – IF (original) Implant exchange – Intramedullary nailing Implant exchange – curved plate and IF Implant exchange – 110 degree blade plate Soft tissue procedure Dynamization Osteochondroplasty											
Hip Dislocation Implant removal Bone graft Wound closure Proximal femur osteotomy Implant exchange – THA Implant exchange – HA Implant exchange – IF (crossover) Implant exchange – IF (original) Implant exchange – Intramedullary nailing Implant exchange – curved plate and IF Implant exchange – 110 degree blade plate Soft tissue procedure Dynamization Osteochondroplasty	Adjudicated Data										
Peri-prosthetic Femur Fracture Implant removal	Adjudicated Data										

Bone graft Wound closure Proximal femur osteotomy Implant exchange – THA Implant exchange – HA Implant exchange – IF (crossover) Implant exchange – IF (original) Implant exchange – Intramedullary nailing Implant exchange – curved plate and IF Implant exchange – 110 degree blade plate Soft tissue procedure Dynamization Osteochondroplasty											
Hip Instability Implant removal Bone graft Wound closure Proximal femur osteotomy Implant exchange – THA Implant exchange – HA Implant exchange – IF (crossover) Implant exchange – IF (original) Implant exchange – Intramedullary nailing Implant exchange – curved plate and IF Implant exchange – 110 degree blade plate	Adjudicated Data										

[figure not shown]
Soft tissue procedure Dynamization Osteochondroplasty											
Wound Healing Implant removal Bone graft Wound closure Proximal femur osteotomy Implant exchange – THA Implant exchange – HA Implant exchange – IF (crossover) Implant exchange – IF (original) Implant exchange – Intramedullary nailing Implant exchange – curved plate and IF Implant exchange – 110 degree blade plate Soft tissue procedure Dynamization Osteochondroplasty	Adjudicated Data										
Screw Penetration Implant removal Bone graft Wound closure Proximal femur osteotomy Implant exchange – THA Implant exchange – HA Implant exchange – IF (crossover) Implant exchange – IF (original) Implant exchange –	Adjudicated Data										

Intramedullary nailing Implant exchange – curved plate and IF Implant exchange – 110 degree blade plate Soft tissue procedure Dynamization Osteochondroplasty											
Screw Cut-Out Implant removal Bone graft Wound closure Proximal femur osteotomy Implant exchange – THA Implant exchange – HA Implant exchange – IF (crossover) Implant exchange – IF (original) Implant exchange – Intramedullary nailing Implant exchange – curved plate and IF Implant exchange – 110 degree blade plate Soft tissue procedure Dynamization Osteochondroplasty	Adjudicated Data										
Post-Traumatic Arthritis Implant removal Bone graft Wound closure Proximal femur osteotomy Implant exchange – THA Implant exchange – HA	Adjudicated Data										

Implant exchange – IF (crossover) Implant exchange – IF (original) Implant exchange – Intramedullary nailing Implant exchange – curved plate and IF Implant exchange – 110 degree blade plate Soft tissue procedure Dynamization Osteochondroplasty											
IT Fracture Implant removal Bone graft Wound closure Proximal femur osteotomy Implant exchange – THA Implant exchange – HA Implant exchange – IF (crossover) Implant exchange – IF (original) Implant exchange – Intramedullary nailing Implant exchange – curved plate and IF Implant exchange – 110 degree blade plate Soft tissue procedure Dynamization Osteochondroplasty	Adjudicated Data										
Relieve Pain Implant removal Bone graft Wound closure Proximal femur	Adjudicated Data										

osteotomy Implant exchange – THA Implant exchange – HA Implant exchange – IF (crossover) Implant exchange – IF (original) Implant exchange – Intramedullary nailing Implant exchange – curved plate and IF Implant exchange – 110 degree blade plate Soft tissue procedure Dynamization Osteochondroplasty											
Femoral Head Necrosis	Adjudicated Data										
Severe Femoral Neck Malunion	Adjudicated Data										
Nonunion	Adjudicated Data										

Figure 3: Kaplan-Meier Curves for Primary Clinical Endpoint (Significant Interaction Between Implant Type and Supplementation Present)

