5.2.2 Primary Analyses

Two independent comparisons between the treatment groups (SHS versus cancellous screws *AND* vitamin D₃ supplementation versus placebo) will be made using the chi-square statistic and an alpha level of 0.05. **Table 3** shows the details for the analysis of primary outcomes.

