5.2.4 Planned Exploratory Analyses

Exploratory analyses will be conducted comparing the treatment effects in participants with undisplaced versus displaced femoral neck fractures, and emergent (<8 hours) versus non-emergent (≥ 8 hours) internal fixation. We plan to fit logistic regression models and include treatment by subgroup interactions to assess whether the magnitude of the treatment effect is significantly different between subgroups. **Table 5** shows the details for the exploratory analyses.

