		Relative Risk Reduction from the SHS and vitamin D supplementation					
		20%	25%	30%	33%	35%	40%
Incidence of Patient Important Outcomes in the control groups	20%	2994	1890	1294	1060	936	706
	25%	2266	1434	984	808	714	540
	30%	1782	1130	778	638	566	428
	35%	1436	914	630	518	460	348
	40%	1178	752	520	428	380	288

- Total sample size required to achieve 80% power for the independent comparisons of the SHS versus cancellous screws AND vitamin D supplementation versus placebo.
- Grey highlighted boxes denote scenarios where we have more than 80% power (alpha=0.05, 2-sided) to detect the hypothesized difference, given our proposed sample size of 808.
- Control groups: cancellous screws and placebo supplementation

Table 3: Summary of Primary Outcome Analyses

Variable/Outcome	Hypothesis for Surgical Treatments	Hypothesis for Nutritional Supplementation	Outcome Measures	Method of Analysis
Re-operation	The incidence of re-operation, femoral head osteonecrosis, severe femoral neck malunion, or nonunion will be lower in patients receiving a SHS compared to cancellous screws.	The incidence of re-operation, femoral head osteonecrosis, severe femoral neck malunion, or nonunion will be lower in patients receiving vitamin D versus placebo.	Re-operation anytime within 12 months	Chi-square statistic with independent comparison for the surgical treatments and nutritional treatments (alpha=0.05)
Femoral head osteonecrosis			Evidence of femoral head osteonecrosis on X-Rays or MRI	
Severe malunion			Evidence of severe femoral neck malunion on X-Rays	
Nonunion			Failure of the fracture to progress towards healing defined as a Radiographic Union Score for Hip (RUSH) ^{41,42} score below a pre-determined threshold specific for nonunion at 6 months or greater post-injury	

[figure not shown]
*The primary outcome is a composite of re-operation, femoral head osteonecrosis, severe femoral neck malunion, or nonunion.

Table 4: Summary of Secondary Analyses

Variable/Outcome	Hypothesis for Surgical Treatments	Hypothesis for Nutritional Supplementation	Outcome Measures	Method of Analysis
HRQL and function	HRQL and function will be better in patients receiving SHS versus cancellous screws.	HRQL and function will be better in patients receiving vitamin D versus placebo.	HOS and SF-12	Summary statistics of means and confidence interval Longitudinal modeling to include treatment and time

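### SAP 8.0 makes the protocol's unconditional primary chi-square tests depend on a non-significant interaction test, and the other branch has neither a rule for a conclusion nor a descriptive label

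*Combined protocol and SAP*

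**What the plan says.** Protocol 5.2.2 says of the two comparisons (implant, supplement) that they "will be made using the chi-square statistic and an alpha level of 0.05". Protocol Table 3 repeats this for the composite: a chi-square statistic "with independent comparison for the surgical treatments and nutritional treatments (alpha=0.05". Neither place attaches a condition. Protocol 5.1 assumes that the two treatments do not modify each other, and Table 2 gives 808 as the total for 80% power on each comparison. The only interactions in the protocol are in 5.2.4, where exploratory models "include treatment by subgroup interactions to assess whether the magnitude of the treatment effect is significantly different between subgroups".

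SAP 8.0 has a different order: "The first analysis of clinical outcomes will be a Cox regression with main effects for implant type and supplementation, and the interaction between the two". Where that interaction is not significant at 0.05, "we will perform two independent comparisons between the treatment groups" by chi-square at 0.05. If it is significant: "If the interaction is significant we will keep this interaction term in all subsequent analyses, and present two hazard ratios (HRs", that is, implant within each supplement group and supplement within each implant group. The results go to SAP Table 12, which as extracted has four hazard-ratio columns (the first is "Surgery X + Supplement X vs. Surgery Y + Supplement X") and one P-value column. SAP 8.0 also says: "The primary analyses will first be completed using only blinded treatment groups".

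**The concern.** An analysis that is primary without condition in the protocol is conditional in the SAP. When the condition fails, the tests that the trial was sized for are not run. Their replacement is two hazard ratios per factor, each comparing about 202 with 202 patients. SAP 8.0 gives an alpha for the interaction and for the chi-square tests, but none for the hazard ratios. It does not say which of them, or how many, would settle the question about an implant or about vitamin D, and it does not say that no claim will be made.

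With no true interaction, about 5% of trials enter this branch. What the primary conclusion would then be is left to whoever reads Table 12. Blinding of the analyst and the Steering Committee (protocol 4.11, SAP 8.0) limits steering toward a favoured arm but does not supply the missing rule.

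**Working it through.** **Inputs.** Control rate 25% and relative reduction 33% (protocol 5.1); 80% power (Table 2); two-sided 0.05 (5.2.1, 5.2.2, Table 2); equal allocation to four groups (4.4), so 808/4 = 202 per cell; cell rates 30%, 20% and 20% (5.1). The double-treatment rate is not stated. I assume 20% × 0.67 = 13.4%.

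**1. The plan's own figure.** With p1 = 0.25, p2 = 0.25 × 0.67 = 0.1675, d = 0.0825 and mean 0.20875:

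n' = [1.960 √(2 × 0.20875 × 0.79125) + 0.8416 √(0.1875 + 0.1394)]² / d² = (1.1265 + 0.4812)² / 0.006806 ≈ 380 per arm (760 in total).

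With continuity correction, n = (n'/4)[1 + √(1 + 4/(n'd))]² ≈ 404 per arm, so 808. Then 808/0.9 = 897.8, so 898. Both stated figures reproduce, for the unconditional marginal comparison. (Section 5.1 prints alpha as 0.5; that would give 270, so 0.05 was used.)

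**2. Per-factor false-positive rate, no true effects.** In a balanced 2×2 design the marginal statistic A and the interaction statistic I are independent standard normals, and a factor's two simple effects are (A ± I)/√2. The error is 0.95 × 0.05 = 0.0475 from the chi-square route, plus P(|I| > 1.96 and the branch rule is met):

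| Rule in the hazard-ratio branch | Added | Total |
|---|---|---|
| No claim | 0 | 4.75% |
| Both significant, same direction | about 0 | 4.75% |
| One pre-named hazard ratio at 0.05 | 0.0169 | 6.4% |
| Either, at 0.025 each | 0.0211 | 6.9% |
| Either, at 0.05 | 0.0325 | 8.0% |

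Allowing opposite directions under the rule that both be significant adds 0.00125 (4.9%), but such a pair is not a coherent claim for a factor. Simulating the SAP procedure with Cox models at 808 patients gave 8.0%, 7.8% and 8.0% for the either-at-0.05 rule at event rates of 25%, 30% and 20%. For at least one factor, the error is 9.3% with no claim and 13.5% with either at 0.05, against 1 − 0.95² = 9.75% for two unconditional tests.

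**3. Power per factor at the planning rates (30/20/20/13.4%, 202 per cell).** The simulation used binomial cells, a pooled chi-square for the marginal test, and log-hazard contrasts with variance 1/events for the interaction and hazard ratios. The gate fires in 5.1% of trials. Power is 83% ungated and 79% gated with no claim. With the continuity-corrected test that reproduces 808, it is 81% and 77%.

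**4. Synergy.** The last sentence of the sample-size text in protocol 5.1 says that synergy would add power. The double-treatment rates below are assumed and stand in neither document; the other cells stay at 30/20/20%.

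| Double-treatment rate | Gate fires | Ungated | Gated, no claim |
|---|---|---|---|
| 13.4% | 5% | 83% | 79% |
| 12% | 6% | 89% | 84% |
| 10% | 13% | 95% | 83% |
| 8% | 30% | 98% | 69% |
| 6% | 57% | 99% | 43% |

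**5. Interaction in the other direction.** At assumed double-treatment rates of 20%, 25% and 30%, ungated marginal power is about 40%, 13% and 5%. A gated rule accepting either hazard ratio at 0.05 has about 58%, 67% and 86%. At 30% each factor has a 10-point effect in both strata, in opposite directions, and the gate fires in 91% of trials.

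**The case against.** The strongest reply is that SAP 8.0 speaks of presenting and reporting hazard ratios with confidence intervals, which is the language of estimation. On that reading the error is below 5%, and every figure above 5% needs a testing rule of the reader's own making. This stands. The general 0.05 criterion in protocol 5.2.1 is not tied to this branch. The single P-value column in Table 12 cannot serve four hazard ratios; it may be for the interaction, or a header broken in extraction. A reader might infer that the plan inflates the false-positive rate to 8%; the documents do not support that.

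The branch is also not unplanned. The trigger, its alpha, the four hazard ratios, the table and the Kaplan-Meier curves are all specified. Without interaction about 95% of trials run exactly the protocol's tests, and 79% is about one point below the 80% target. Moderate synergy (12% or 10%) leaves no-claim power above its planning-rate value, so it would be wrong to say that synergy generally costs power under the gate. Checking the independence assumption is sound, and step 5 shows that marginal tests can miss a strong less-than-additive or qualitative interaction.

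This does not remove the point. The estimation reading is natural but unstated, and on it no primary conclusion is drawn in that branch. A no-claim gate can never have more power than the ungated test, because it only discards rejections. The advantage in step 5 belongs to a testing rule that the SAP does not contain.

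**Conclusion.** The concern holds as a conflict between the documents and a missing rule, and it should be fixed. SAP 8.0 makes conditional what protocol 5.2.2 and Table 3 make unconditional. For the branch it adds, it states neither how a conclusion is reached nor that none is drawn. On the natural reading the cost is power: about 83% to 79% at the planning rates (81% to 77% with continuity correction), and much more under strong synergy, so the protocol's synergy sentence is not reliable under the gate. Inflation to between 6.4% and 8.0% is possible only under testing rules that neither document states.

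The power figures assume 808 evaluable patients, a double-treatment rate of 13.4% at planning, and the other double-treatment rates as marked. The shell of SAP Table 2 prints a total of 86 patients. At that size marginal power would be about 16%, and the error under the either-at-0.05 rule about 6.6% to 7.7%. The departure from the protocol does not depend on the sample size.

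**What to change.** In SAP 8.0, make the two marginal chi-square comparisons primary unconditionally, as in protocol 5.2.2. Always report the implant-by-supplement interaction with its 95% confidence interval, and the four simple effects, beside the primary result. Label Table 12 descriptive, with no significance claims. In protocol 5.1, tie the synergy sentence to the marginal analysis.

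If the gate is kept, SAP 8.0 should state one decision rule and alpha per factor with its power, or state that no primary conclusion is drawn in that branch. Protocol 5.2.2 should then be amended to match.

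The cost is wording only; no data or patients are affected. The downside of the preferred change is the low marginal power under a strong less-than-additive or qualitative interaction (step 5), which is why the interaction and simple effects must always be shown.
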